Dosimeter Location and Measured Effective Radiation Dose in Pain Management Physicians

NCT06309407

May 7, 2024

1. Protocol Title:

Dosimeter Location and Measured Effective Radiation Dose in Pain Management Physicians

2. Objectives

The primary objective is to determine if there is a significant difference in radiation readings between dosimeters worn on the chest versus the hand of interventional pain management physicians and elucidate which dosimeter had higher readings.

The secondary objectives are to examine trends in radiation exposure in each group (chest only or chest plus hand) over the course of the study to understand if overall radiation exposure decreases over time due to changes in practice habits as a response to exposure reports. The last objective will be to track incidences of physician glove breaches in both groups to assess if wearing hand dosimeters is associated with an increased risk of the event.

3. Background

Radiation producing imaging use is ubiquitous in medicine with a wide range of imaging modalities. Of these, computed tomography (CT) and fluoroscopy are the most commonly used and are associated with some of the highest radiation exposure for patients and operators.¹⁻² This is particularly important in fields such as Interventional Pain Management where these modalities are essential to daily practice. The utilization of opioid-sparing minimally invasive techniques for low back pain and arthritis using CT and fluoroscopy has expanded over the years which has greatly increased radiation exposure among pain specialists.

Current Occupational Safety & Health Administration (OSHA) guidelines for occupational dose limitations indicate that the total maximum effective dose to the head and trunk is 12.5 mSv per calendar quarter and 187.5 mSv per quarter for the hands and feet.⁴ Complications of acute and chronic radiation exposure can include tissue reactions such as skin burns and cataracts or stochastic affects like cancer or hereditary derangements.⁵

Spatial relationship to the imaging device, imaging type, and technical execution of the procedure all affect the amount of radiation physicians and patients are exposed to. In terms of equipment location, the highest levels of radiation in C-arm fluoroscopy is very close to the physician's waist and abdomen.⁶ Discrepancy in exposure among imaging type is noted by Hoang et al who showed that CT guided techniques have approximately half the effective dose to physicians compared to conventional fluoroscopy techniques.¹² However this is not without a tradeoff, as procedures such as epidural steroid injections under CT guidance are associated with more than eight times the radiation dose to patients as compared to fluoroscopy guided.¹³ Thankfully, techniques that incorporate the benefits of both such as ultralow-dose CT are being popularized, which actually has a lower dose than traditional fluoroscopy to the patient.²²

As one might imagine, this highly variable and multifaceted nature of radiation exposure can potentially lead to large effective doses at one time. Several studies from other specialties found that the radiation exposure to vulnerable body parts like the eyes, thyroid, and hands often meet acceptable levels but could be easily and significantly affected based on physician practices; particularly by the improper use of personal protective equipment, patient positioning, and work ergonomics.¹⁶⁻¹⁹ Perhaps unsurprisingly, a review by Martin shows that, in radiologists and cardiologists, the hands are the part of the body most affected by work practice and positioning when it comes to radiation exposure and the author highly recommends the use of a hand dosimeter.²⁰ Stoeckelhuber et al. noted that interventionalists performing procedures under CT that expose their hand to the primary beam can receive an effective radiation dose of up to 0.6 mSv in procedures lasting only 20 seconds.⁸ At this rate, if a physician were to use fluoroscopy in this manner for a two-minute procedure, they would only be able to safely perform a mere 52 procedures per calendar quarter to maintain OSHA safety standards.

The use of multiple protective measures such as long needle holders, protective gloves, and lead drapes is considered the gold standard in practice and have been shown to decrease dose rates by up to 99.6% overall.^{8,14} Similarly, Hoffler et al found that, when compared to no protective measures, just the use of attenuating gloves and leaded eye protection can reduce the radiation exposure to the hands and eyes by 69.4% and 65.6% respectively.²¹ However, in a survey of 708 interventional pain physicians, 93% stated they were concerned with radiation exposure but only 63% had formal safety training and there was low overall understanding of evidence-based radiation safety practices.⁹ Therefore, better understanding of a physician's individual practices on effective radiation dose through a quality improvement study will help to close gaps in knowledge and understanding of exposure.

A dosimeter is a small device which measures the radiation the physician receives from their practice. There are several different kinds of dosimeters including the commonly worn chest monitor and others closer to the hands of the physician, such as wrist bands or rings. Carinou et al indicate that these devices are overall generally accurate at measuring the correct radiation dose but have their limitations depending on the manufacturer, scope of intended use, and material composition.¹⁵ There are currently no studies comparing dosimeter location and radiation exposure readings in pain management physicians. The effective dose detected by a single chest monitor is likely not an accurate representation of the doses received in other parts of the body in pain management physicians. There are also no published studies assessing the risk of wearing hand dosimeters in sterile procedures, such as increased frequency of glove breaches or procedure-related infections.

Of the various factors that influence radiation exposure risk, dosimeter location on a proceduralists body is of particular interest to interventional pain physicians. Yamashita et al. found a large discrepancy in dosimeter readings among spine surgeons using fluoroscopy between the dosimeters worn on the chest (125.6 mSv) and those worn on the thumb (368 mSv).¹⁰ This discrepancy indicates that the hands of proceduralist may be exposed to radiation exceeding the acceptable safe limit despite a chest worn dosimeter measuring safe radiation levels. This has obvious and dangerous implications for individuals that only wear

a chest dosimeter.

Our review of literature identifies a knowledge gap between dosimeter location and radiation risk among interventional pain physicians. This evidence supports the need of a quality improvement study to further assess radiation exposure in pain management physicians. In order to ensure physician safety, it is crucial to have adequate radiation exposure training and protective equipment as well as accurate measurements of effective radiation dose. This is particularly important with parts of the body such as the hands where effective radiation dose may be much higher than being recorded on chest dosimeters. This quality improvement study will be essential to providing valuable insight into radiation exposure and may help guide safety protocols in the future for OHSU physicians.

In sum, the variability in effective radiation dose based on procedure type, imaging modality, protective equipment and procedural approach requires further investigation into dosimeter location to accurately evaluate provider safety during radiation generating procedures.

4. Study Design

This is a prospective quality and safety improvement study designed to examine potential differences in radiation measurements depending on dosimeter location on an interventional pain medicine practitioner's body. The comparison will be made between a group wearing chest worn dosimeters (control) and chest plus hand worn dosimeters (experimental) between October 1, 2022 and April 21, 2023.

The study will be performed at the Comprehensive Pain Center at Oregon Health and Science University (OHSU) and involve attending physicians and fellow physicians who consent to participate. The physicians who consent will then be randomly assigned by a computer-generated program to either the control group (chest dosimeter) or experimental group (chest plus hand dosimeter).

The control group will be assigned a chest dosimeter to wear while the experimental group will be assigned a hand and chest dosimeter. The dosimeters will be collected according to standard processing protocol every three month(s) by the designated Comprehensive Pain Center dosimeter collector. The badges will then be submitted to the vendor, Mirion, who will process the dosimeters and return an electronic report available for viewing online and at the procedure area nursing station. All study participants will also be emailed a copy of the report.

The study team will assess physician compliance with wearing the dosimeter(s) by having the procedure nurses perform a daily written audit of chest and hand dosimeter presence or absence.

Radiation measurements and compliance logs will be recorded in OHSU Microsoft Teams

Excel. We are done collecting data. We are using Microsoft Excel in Teams to input and analyze the data. Data analysis will be performed by an OHSU statistician.

Consistent with the OHSU standards for wearing hand dosimeters for sterile procedures, for each procedure the physician wearing the hand dosimeter will be required to:

- 1) Wash the hand dosimeter with one pump (2 mL) of Avaguard
- 2) Place the hand dosimeter on a bare hand
- 3) Dispense one pump (2 ml) into the palm of one hand. Dip fingertips of the opposite hand into the hand prep and work under fingernails. Spread remaining hand prep over the hand and up to just above the elbow.
- 4) Dispense one pump (2 ml) and repeat procedure with opposite hand.
- 5) Dispense final pump (2 ml) of hand prep into either hand and reapply to all aspects of both hands up to the wrists. Allow to dry. Do not use towels to dry.
- 6) Double glove both hands using sterile gloves.

At the conclusion of each procedure, the physicians in both groups will be required to inspect their surgical gloves for any visible breaches. All breaches of one or both gloves on each hand that are recognized during or after the procedure must be reported to the study team. The physician will also indicate on which hand the hand dosimeter, if applicable, was worn.

5. Study Population

Inclusion and Exclusion Criteria

Inclusion criteria includes:

- a. Physicians actively performing fluoroscopy procedures at the OHSU Comprehensive Pain Center.

Exclusion criteria includes:

- a. Those that do not want to participate in the quality improvement project.

Number of Subjects

Of 6 attending physicians and 4 fellows that qualify for the study, we anticipate 8 participants in the study.

Vulnerable Populations

- a. Vulnerable populations are not involved in this quality improvement study.

6. Setting

The study examines radiation exposure of OHSU physicians performing their routine medical practice at the OHSU Comprehensive Pain Center Procedure Rooms 1 and 2. Hand dosimeters are currently used at OHSU in other departments. All study activities will take place at OHSU or remotely using OHSU provided secure computers, by OHSU personnel.

7. Recruitment Methods

Volunteers will be recruited through OHSU email. Consent to participate will be collected prior to the start of the study.

8. Consent Process

Participants will be de-identified in OHSU Microsoft Teams Excel. Individual consents will be obtained from Comprehensive Pain Center physicians prior to the start of the data collection period. For all procedure patients, standard procedure informed consent will be obtained.

9. Procedures

The study team will directly input data collected from dosimeters and compliance reports into OHSU Microsoft Teams Excel.

The variables that will be recorded in OHSU Microsoft Teams Excel **for each participant** will include:

- a. Group identifier – control or experimental
- b. Chest dosimeter radiation exposure reading (Total Effective Dose Equivalent in rem) for each 3-month period
- c. Hand dosimeter radiation exposure reading (Total Effective Dose Equivalent in rem) for each 3-month period
- d. Dosimeter compliance for each 3-month period (%)
- e. Report(s) and date(s) of glove breaches during the procedure

10. Data and Specimens

Handling of Data and Specimens

No specimens will be collected for this study. OHSU Microsoft Teams Excel will be used for data collection and storage. No identifiers will be collected that could link the participant to published data. Access to data is restricted to study personnel and access to data requires OHSU ID/password authentication.

11. Sharing of Results with Subjects

The study results will be published.

12. Data and Specimen Banking

Data will not be stored for future research. Data will be retained for up to 3 years or until the study is completed and results are published.

13. Data Analysis

For the statistical analysis, to perform hypothesis testing, the statistician will use a t-test between dosimeter type and effective radiation dose.

The statistician will perform an analysis using descriptive statistics, tables, and data visualization techniques. The statistics will include median (min, max) and mean (SD) with 95% confidence intervals for continuous variables and frequencies and proportions for binary and categorical variables. The statistician will use multiple imputation to address missing data if the missing rate is more than 10%. Multiple imputation by chained equations (MICE)

is implemented assuming missing at random.

14. Privacy, Confidentiality and Data Security

Access to data during the study period is restricted to study personnel and access to data requires OHSU ID/password authentication.

Data for this project will be stored in Microsoft Teams Excel

The study team will not collect protected health information.

Standard institutional practices will be followed as described by the OHSU Information Security Directives at the following link:

<http://www.ohsu.edu/xd/about/services/integrity/policies/ipspolices-info-sec-directiv.cfm#results> to maintain the confidentiality and security of data collected in this study.

Study staff will be trained with regard to these policies. Electronic data will be stored on encrypted: computers, laptops, tablets, and iPads.

Electronic data is stored:

- On restricted drives on the OHSU network.
- OHSU Microsoft Teams Excel

Access to data is restricted to study personnel. Access to data requires OHSU ID/password authentication.

15. Risks and Benefits

a. Risk

There is a risk of breach of confidentiality. There is no increased risk of radiation exposure to participants as they will not be asked to modify their routine medical practice in any way. There is a risk of hand dosimeters being associated with a glove breach. To address this risk, all physicians wearing hand dosimeters will be required to double glove per OHSU standards. There is no evidence of dosimeters causing increased risk to patients and standard procedure consent will be obtained per routine medical practice as is consistent with OHSU departments using hand dosimeters.

b. Potential Benefits to Participants

Identifying a discrepancy in radiation exposure between chest dosimeters and hand dosimeters that could lead to changes in provider radiation safety.

References

medical doctors. *Insights into Imaging* 12.. doi:10.1186/s13244-021-01041-2

- 4. Occupational Safety and Health Administration, (n.d.), Ionizing Radiation Standards, United States Department of Labor, <https://www.osha.gov/ionizing-radiation/standards>
- 6. Schueler BA. Operator shielding: how and why. *Tech Vasc Interv Radiol*. 2010 Sep;13(3):167-71. doi: 10.1053/j.tvir.2010.03.005. PMID: 20723831.

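### Only chest-plus-hand physicians (about 4 of 8) can supply the primary hand-versus-chest contrast, and Section 13 does not define the t-test as a paired, physician-level analysis in that group

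*Combined protocol and SAP*

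**What the plan says.** The primary objective in Section 2 is to "determine if there is a significant difference in radiation readings between dosimeters worn on the chest versus the hand" of interventional pain physicians. Section 4 randomises consenting physicians by computer to two groups and frames the study's comparison as one between those groups. On equipment it says: "The control group will be assigned a chest dosimeter to wear while the experimental group will be assigned a hand and chest dosimeter". It gives no allocation ratio, blocking or stratification.

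Section 5 gives the size as a head count: "Of 6 attending physicians and 4 fellows that qualify for the study, we anticipate 8 participants in the study". Badges are collected every three months, and the study runs "between October 1, 2022 and April 21, 2023". Section 9 lists a chest and a hand reading for each three-month period among the variables recorded for every participant.

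Section 13 tests hypotheses with a t-test relating dosimeter type to dose. It does not mention pairing, the analysis set or how a physician's repeated quarters are handled. It also brings in multiple imputation by chained equations, under missing at random, once more than 10% of values are missing. Section 4 adds: "We are done collecting data".

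**The concern.** The randomised comparison (chest only versus chest plus hand) is not the comparison that the primary objective asks for. Randomisation decides who wears a hand badge. It does not create the hand-versus-chest contrast, which exists only inside physicians who wear both.

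Because Section 13 leaves the t-test open, three things could go wrong in the analysis:

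- Control chest readings enter an unpaired test, so the estimate carries differences between physicians as well as badge location.
- The result is reported as resting on 8 participants, or on 8 physician-quarters treated as independent, when it rests on about 4 physicians.
- Hand readings for control physicians are treated as missing and imputed, although no such readings were ever to be taken.

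**Working it through.** **Inputs from the documents.** 8 physicians anticipated (Section 5); hand badge in one group only, exchange every three months (Section 4); 1 October 2022 to 21 April 2023 = 203 days = two full quarters (182 days) plus 21 days.

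**Assumptions, because the documents give no figure.** 4:4 allocation; two-sided alpha 0.05; results in SDs of a one-quarter hand-minus-chest difference on the log scale; rho, the correlation of a physician's difference between quarters, from 0 to 1. The figure of 8 has no power calculation behind it, so there is nothing to reproduce.

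**1. Readings per quarter at 4:4**

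| Group | Chest | Hand | Pairs |
|---|---|---|---|
| Chest only | 4 | 0 | 0 |
| Chest plus hand | 4 | 4 | 4 |

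**2. What each form of the t-test estimates.** Write h and c for log hand and log chest readings.

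- Paired, experimental group: mean(h − c). Whatever scales both of a physician's readings, such as caseload, cancels.
- Unpaired, experimental hand against control chest: mean(h, experimental) − mean(c, control) = mean(h − c, experimental) + [mean(c, experimental) − mean(c, control)]. The bracket is the difference in chest exposure between two sets of physicians. Randomisation centres it on zero only if wearing a hand badge does not alter practice, and with 4 against 4 it need not be small in the actual sample. Section 3 itself stresses how strongly exposure varies with procedure, modality, protection and technique.
- Group against group on chest readings: contains no hand reading, so it does not address the primary objective.

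**3. Precision of the paired analysis.** With 4 physicians averaged over 2 quarters, the variance of the mean is (1 + rho)/8. Half-width = t(0.975, 3) × √((1 + rho)/8), with t = 3.182. Power is from the exact noncentral t.

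| rho | 95% CI half-width | Detectable at 80% power | Power for 1 SD |
|---|---|---|---|
| 0 | 3.182 × √(1/8) = 1.13 | 1.50 | 49% |
| 0.5 | 3.182 × √(1.5/8) = 1.38 | 1.84 | 36% |
| 1 | 3.182 × √(2/8) = 1.59 | 2.13 | 29% |

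Treating the 8 physician-quarters as independent would give a nominal 2.365 × √(1/8) = 0.84 on 7 degrees of freedom, which is right only at rho = 0. A physician-level sign or signed-rank test on 4 pairs cannot go below p = 2/2⁴ = 0.125.

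**4. Sensitivity to allocation.** Under unrestricted randomisation of 8, an exact 4:4 split has probability 70/256 = 27%, and 3 to 5 hand wearers 182/256 = 71%. At rho = 1 the half-width is 2.48 SD with 3 wearers and 1.24 SD with 5.

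**5. Imputation trigger.** In each quarter, 4 of 8 hand fields are empty by design (50%), or 4 of all 16 reading fields (25%). Either count exceeds 10%.

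**6. Swap of arms at the first exchange (future study only).** Hand badges: 4 × 2 = 8 as planned, 4 + 4 = 8 with the swap. Each of 8 physicians gives one pair, so the variance is 1/8 and the half-width 2.365 × √(1/8) = 0.84. Against the planned design, the ratio is 0.836/1.125 = 0.743 at rho = 0 and 0.836/1.591 = 0.525 at rho = 1, that is, 26% to 47% narrower. At rho = 0 both variances are 1/8, so the 26% comes only from 2.365/3.182.

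**The case against.** The strongest reply is that the parallel groups are there for other stated objectives. Section 2 wants exposure trends followed in each group and glove breaches compared between groups, and both need physicians without a hand badge. The figure of 8 is a head count of participants; the plan never calls it the n of the primary contrast. The statistician may intend a paired test all along. Nor is inadequacy shown: the spine-surgeon figures cited in Section 3, 368 against 125.6 mSv, give a log ratio of ln(2.93) = 1.08. Four physicians would have at least 80% power for that if the SD of physician-level log ratios were at most 1.08/2.13 ≈ 0.5, a value that the documents neither give nor exclude.

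All of this stands, and it limits the point. A reader might infer that the parallel design is an error and that a swap at the exchange would simply have been better. The documents do not support that. The window holds about two quarters, so after a swap no physician stays in one group for two full periods, each physician's change over time is mixed with the change of badge, and the trend-by-group objective is largely lost. A lost hand reading would also remove that physician's only pair. The swap cannot be applied now in any case. Issuing hand badges to former controls for a further quarter would add non-concurrent pairs, collected after exposure reports had been circulated, under no stated rule for extension.

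It would also be too strong to say that control chest readings cannot enter the analysis. They can enter an unpaired test, which is why the test needs to be defined.

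None of this settles what Section 13 leaves open: pairing, analysis set, unit and the treatment of hand readings absent by design.

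**Conclusion.** The point holds as a gap in the definition of the primary analysis. It does not show that the design was wrong or that the study is inadequately powered. The objective is "significant difference in radiation readings between dosimeters worn on the chest versus the hand", only one arm yields hand readings, and the t-test as written does not isolate badge location.

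The primary estimate rests on about 4 physicians and 3 degrees of freedom, with a 95% half-width of 1.13 to 1.59 SD. These figures assume 4:4 allocation, two complete quarters per physician and two-sided 0.05; the range reflects the unknown rho. The need for a paired analysis and for keeping control hand readings out of imputation does not depend on any of these assumptions. The 26% to 47% gain from a swap further assumes no carryover and no lost readings.

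**What to change.** In Section 13, with data collection closed:

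- Define the primary analysis as a paired, physician-level analysis of the log hand:chest ratio, averaged over each physician's quarters, in chest-plus-hand physicians only. Back-transform to a ratio with its 95% confidence interval.
- Report the actual number of physicians and degrees of freedom for this contrast (about 4 and 3), separately from the 8 participants in Section 5.
- State that control physicians' hand readings are absent by design, do not count towards the 10% missing rate and are not imputed.
- Keep any comparison that uses control chest readings as descriptive or secondary.
- Say how a zero reading is handled, since a log ratio needs positive values, and record that this definition was written after data collection and whether results had been seen.

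The cost is SAP wording only. The downside is that the stated n and precision for the primary contrast become less favourable.

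For a future study only, swapping arms at the three-month exchange would give every physician a pair with the same number of hand badges at 4:4. The price is largely losing the trend-by-group objective, with possible carryover from exposure reports.

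### The exposure-trend and glove-breach objectives have no procedure denominator, so a change in caseload can look like a change in practice habits and breach risk by group has no defined base

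*Combined protocol and SAP*

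**What the plan says.** Section 2 sets two secondary objectives. The first is to learn whether "overall radiation exposure decreases over time due to changes in practice habits as a response to exposure reports". The second is to track glove breaches in both groups and "assess if wearing hand dosimeters is associated with an increased risk of the event".

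Section 9 lists five variables per participant: group, a chest reading, a hand reading, dosimeter compliance as a percentage, and reports and dates of glove breaches. The readings are totals for a badge period: "Chest dosimeter radiation exposure reading (Total Effective Dose Equivalent in rem) for each 3-month period". The list is introduced as what the variables will include, so it may not be exhaustive. Even so, no section mentions a procedure count, fluoroscopy time or clinic days.

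Section 4 has nurses audit badge presence daily and says "Radiation measurements and compliance logs will be recorded in OHSU Microsoft Teams" Excel. It also requires glove inspection after each procedure in both groups, but only breaches have to be reported. Of the exposure reports it says "All study participants will also be emailed a copy of the report".

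Section 13 plans one t-test, of dosimeter type against dose. Everything else is descriptive, including frequencies and proportions for binary variables. It names no denominator, rate, offset or workload covariate.

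**The concern.** A badge total is dose per procedure multiplied by the number of procedures. The trend objective concerns the first factor (how physicians work), but the recorded data show only the product. A quieter second period could be read as physicians responding to their reports, and a busier one could hide a real improvement.

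The breach objective has a related gap. Each procedure is an opportunity for a breach, so risk needs the number of procedures inspected. Without it, the group that did more procedures will tend to show more breaches at the same risk per procedure.

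Section 11 says the results will be published, and Section 3 hopes that they will guide safety protocols. A misattributed trend or breach difference could therefore influence practice.

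**Working it through.** **1. The protocol's own link between caseload and quarterly dose.** Section 3 gives 0.6 mSv for 20 seconds of hand exposure in the primary beam, a two-minute procedure, and a hand limit of 187.5 mSv per quarter.
- Dose per procedure: 0.6 × 120/20 = 3.6 mSv.
- Procedures to reach the limit: 187.5/3.6 = 52.08.

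This reproduces the statement that "they would only be able to safely perform a mere 52 procedures per calendar quarter to maintain OSHA safety standards". The example is an extreme hand exposure and says nothing about the size of chest readings here. It does show that the protocol itself treats a quarterly total as dose per procedure times number of procedures.

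**2. What a fall in the total can mean.** Suppose a total falls by 20% (an illustrative value). Then

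change per procedure = 0.80/(1 + caseload change) − 1.

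| Assumed caseload change | Implied change in dose per procedure |
|---|---|
| −30% | 0.80/0.70 − 1 = +14% |
| −20% | 0.80/0.80 − 1 = 0% |
| −10% | 0.80/0.90 − 1 = −11% |
| 0% | −20% |
| +10% | 0.80/1.10 − 1 = −27% |

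The same badge data fit worse practice, unchanged practice or better practice. Random allocation does not help, because the trend compares each physician with himself or herself over time.

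**3. Length of the observation window.** Section 4 gives "between October 1, 2022 and April 21, 2023". Counted inclusively, this is 92 + 90 + 21 = 203 days. Section 4 says badges are collected every three months but gives no exchange dates. If exchanges followed calendar quarters (an assumption), a third reading that stopped at the study end would cover 21 days, and its total would be low for that reason alone.

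**4. Breaches by group.** At equal risk per procedure, the ratio of expected breach counts equals the ratio of procedures. About 8 physicians are expected (Section 5), and Section 4 states no allocation ratio, blocking or stratification. I simulated physician caseloads with a 4:4 split (400,000 draws, gamma and lognormal distributions). The split and the between-physician CV are assumptions.

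| Assumed caseload CV | Median imbalance between groups | Chance of at least 1.25-fold |
|---|---|---|
| 0.3 | 1.15-fold | 29% |
| 0.5 | 1.26- to 1.27-fold | 52% to 53% |

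**5. Whether a recorded variable could stand in for caseload.** The compliance percentage shows whether badges were worn, not how many procedures were done. The audit logs might yield days audited, but days are not procedures.

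**The case against.** There is a fair case on the other side.

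- The first objective speaks of overall exposure, and the limits cited in Section 3 are per quarter. The unadjusted total is therefore a legitimate endpoint. **This stands**, and only the attribution to habits is affected.
- The breach objective claims association only, and Section 13 plans no breach test. A reader might infer that the plan would report a caseload difference as an effect of hand dosimeters. The text does not go that far. **This stands.**
- Section 13 plans proportions, and a proportion has a denominator. **This stands in part**: the denominator could be physicians or procedures, and the plan does not say which. A proportion of physicians would still ignore the number of procedures at risk.
- Unequal group sizes might seem to inflate breach ratios further. That would assume an allocation method the documents do not state, and dividing by the number of physicians would remove it. **It is no part of this point.**
- Procedure counts would not justify the causal wording. **This stands**: every participant receives the reports, so there is no comparison group without feedback.
- Chance variation in few breaches may matter as much as caseload. **This stands**, and it is a reason for an interval rather than for omitting the denominator.

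A reader might also extend the point to the primary chest-versus-hand comparison. Within one physician wearing both badges, caseload is shared, so the documents do not support that extension in general. It would arise only if the comparison were made between groups or if wear of the two badges differed.

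**Conclusion.** The point holds for the two secondary objectives. As planned, the data cannot separate a change in practice from a change in caseload, and breach risk has no defined denominator. Confidence is high for the omission, because no section lists a procedure count or a workload adjustment.

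The size is illustrative. A caseload change passes into the total one for one if dose per procedure is constant. The 29% to 53% chance of a 1.25-fold imbalance rests on an assumed 4:4 split and assumed CVs of 0.3 to 0.5. The same figures leave a 47% to 71% chance of a smaller imbalance.

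The point does not show that any actual trend or breach difference is due to caseload. It should be addressed before the secondary results are interpreted, but it does not undermine the study as a whole.

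**What to change.** 1. Add to Section 9 the number of fluoroscopy procedures per physician per badge period, from existing records if they can be retrieved and linked.
2. Report the trend both as the three-month total and as dose per procedure, paired within physician, over full badge periods of equal length. State the exchange dates. Show any partial period separately or per procedure.
3. If readings fall below detection, keep those pairs and show bounds or a censored-data summary. Dropping them selects on the outcome: under assumed lognormal doses with 20% of first readings below detection, a true 20% fall appeared as about 15% to 18% among the retained pairs.
4. Report breaches per procedure by group, with an interval that allows for clustering by physician. Note that Section 15 requires double gloving of those wearing hand dosimeters, so a rate cannot separate the dosimeter from the gloving.
5. Describe the trend objective as change over time, without a stated cause, whether or not counts are obtained.
6. If counts cannot be retrieved, report both objectives descriptively, with no attribution to practice change or dosimeter wear.

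The cost is a small retrospective data pull: 8 physicians × 2 periods = 16 counts, if there are two full periods. Section 4 says data collection has ended and Section 8 that participants are de-identified in the study file, so the pull may fail. Items 5 and 6 need only wording. Case-mix differences would remain, and intervals from about 8 physicians would be wide.
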